4.2.7 Subject Exclusion Criteria

The subject must be excluded from participating in the trial if the subject:

- 1. Is currently participating and receiving study therapy or has participated in a study of an investigational agent and received study therapy or used an investigational device within 4 weeks or 5 half-lives of the first dose of treatment, whichever is shorter.
- 2. Has a diagnosis of immunodeficiency or is receiving systemic steroid therapy that exceeds a maximum amount of 10mg of prednisone/day or any other form of immunosuppressive therapy within 7 days prior to the first dose of trial treatment.
- 3. Has a known history of active TB (Bacillus Tuberculosis)
- 4. Hypersensitivity to pembrolizumab or any of its excipients.
- 5. Has had a prior anti-cancer monoclonal antibody (mAb) within 4 weeks prior to study Day 1 or who has not recovered (i.e., ≤ Grade 1 or at baseline) from adverse events due to agents administered more than 4 weeks earlier.
- 6. Has had prior chemotherapy, targeted small molecule therapy other than pre-specified allowed agents detailed in section 4.2.6, or who has not recovered (i.e., ≤ Grade 1 or at baseline) from adverse events due to a previously administered agent.
 - Note: Subjects with ≤ Grade 2 neuropathy are an exception to this criterion and may qualify for the study.
 - Note: If subject received major surgery, they must have recovered adequately from the toxicity and/or complications from the intervention prior to starting therapy.
- 7. All major surgery including prior surgery to the brain within 3 weeks of commencement of study therapy.
- 8. Has a known additional malignancy that is progressing or requires active treatment. Exceptions include basal cell carcinoma of the skin or squamous cell carcinoma of the skin that has undergone potentially curative therapy or in situ cervical cancer.

- 9. Subjects with previously treated brain metastases may participate provided they are not using escalating steroids for brain metastases at the time of trial consent and study drug initiation, and there remains a measurable lesion in the CNS, as per section 4.2.6.
- 10. Has active autoimmune disease that has required systemic treatment in the past 2 years (i.e. with use of disease modifying agents, corticosteroids or immunosuppressive drugs). Replacement therapy (e.g. thyroxine, insulin, or physiologic corticosteroid replacement therapy for adrenal or pituitary insufficiency, etc.) is not considered a form of systemic treatment.
- 11. Has history of (non-infectious) pneumonitis that required steroids, evidence of interstitial lung disease or active, non-infectious pneumonitis.
- 12. Has an active infection requiring systemic therapy.
- 13. Prior disease progression on anti-PD-1 therapy
- 14. Has a history or current evidence of any condition, therapy, or laboratory abnormality that might confound the results of the trial, interfere with the subject's participation for the full duration of the trial, or is not in the best interest of the subject to participate, in the opinion of the treating investigator.
- 15. Has known psychiatric or substance abuse disorders that would interfere with cooperation with the requirements of the trial.
- 16. Is pregnant or breastfeeding, or expecting to conceive or father children within the projected duration of the trial, starting with the pre-screening or screening visit through 120 days after the last dose of trial treatment.
- 17. Has a known history of Human Immunodeficiency Virus (HIV) (HIV 1/2 antibodies).
- 18. Has known active Hepatitis B (e.g., HBsAg reactive) or Hepatitis C (e.g., HCV RNA [qualitative] is detected).
- 19. Has received a live vaccine within 30 days of planned start of study therapy.
- 20. Contraindication to MRI.
- 21. Patients with a condition related to their cancer or leptomeningeal disease requiring urgent intervention that has not been clinically managed or stabilized prior to the time of consent.
- 22. Brain metastases with risk of mass effect that would contraindicate lumbar puncture, as detailed in section 6.1.2.8.3.
- 23. Live vaccines within 30 days prior to the first dose of trial treatment. Note: Seasonal influenza vaccines for injection are generally inactivated flu vaccines and are allowed;

however intranasal influenza vaccines (e.g., Flu-Mist®) are live attenuated vaccines, and are not allowed.

4.2.8 Eligibility Screening [1]

Eligible patients will be reviewed at the weekly Johns Hopkins Neuro-Oncology Multidisciplinary Tumor Board for unbiased confirmation of diagnosis and treatment candidacy prior to enrollment.

4.2.9 Patient Registration Procedures [SEP]

4.2.9.1. General Registration Guidelines [SEP]

All patients entered on any Johns Hopkins trial, whether treatment, companion, or cancer control trial, must be registered with the Sidney Kimmel Comprehensive Cancer Center and complete Informed Consent. Patients will be registered through CRMS and must be registered prior to the initiation of treatment.

4.2.9.2 Recruitment

- Patients will be recruited through the Brain Cancer Program and the Upper Aerodigestive Division (UAD) at Johns Hopkins Medicine. Patients will be recruited from the Sidney Kimmel Comprehensive Cancer Center and 1-2 other participating sites if accrual is slow.
- Patient referrals will be accepted from other Johns Hopkins Medicine sites which include The Johns Hopkins Hospital, Johns Hopkins Bayview Medical Center, Howard County General Hospital, Sibley Memorial Hospital, and Suburban Hospital, and the other site.
- In addition, Johns Hopkins coordinates the Johns Hopkins Clinical Research Network (JHCRN) which was founded in 2009 as an integrated network of select academic and community-based medical institutions established within the Johns Hopkins Institute for Clinical and Translation Research. The JHCRN is comprised of the 6 hospitals within the Johns Hopkins Medicine, Anne Arundel Medical Center, Greater Baltimore Medical Center, INOVA Health Systems, Peninsula Regional Medical Center and Reading Hospital and Health System.
- Referrals from clinicians at these or other facilities will be accepted. In such a case, communication will be directed to the Principal Investigator of the study. This contact may be in the form of telephone, email, etc. The Principal Investigator may inquire as to patient age, diagnosis, prior treatment, timing of prior treatment, and extent of current disease to determine whether the patient would meet global criteria for the study. This information will not be collected, maintained or stored in any way. Patients referred in such a manner will be required to meet in person for review of eligibility, registration and informed consent. These patients will be referred to the study team members in the Brain Cancer Program and UAD Program at the Johns

Hopkins main campus to review eligibility.

- Additional potential participants will be identified during routine clinic visits to the UAD and Brain Cancer Program at Johns Hopkins. Individuals will be approached by the provider or study team to determine willingness to learn more about a study for which they may be eligible. Discussions regarding study participation will take place privately and individuals will be provided with the IRB approved consent form.
- In addition, potential participants may contact the study team directly. This contact may be in the form of telephone, email, etc. Initial discussions regarding study

4.3 Trial Treatments

The treatment to be used in this trial is outlined below in Table 4:

Table 4: Trial Treatment

Drug	Dose/Potency	Dose	Route of	Regimen/Treatment Period	Use
		Frequency	Administration		
Pembrolizumab	200 mg	Q3W	IV infusion	Day 1 of each 3 week cycle	Experimental

Trial treatment should begin on the day of registration or as close as possible to the date on which treatment is allocated/assigned.

4.3.1 Dose Selection/Modification

4.3.1.1 Dose Selection

The rationale for selection of doses to be used in this trial is provided in Section 4.0 – Background and Rationale.

Details on preparation and administration of pembrolizumab (MK-3475) are provided in the Pharmacy Manual.

4.3.1.2 Dose Modification (Escalation/Titration/Other)

Adverse events (both non-serious and serious) associated with pembrolizumab exposure may represent an immunologic etiology. These adverse events may occur shortly after the first dose or several months after the last dose of treatment. Pembrolizumab must be withheld for drug-related toxicities and severe or life-threatening AEs as per Table 5 below. See Section 4.7 for supportive care guidelines, including use of corticosteroids.

Table 5. Dose Modification Guidelines for Drug-Related Adverse Events

Toxicity	Hold Treatment For Grade	Timing for Restarting Treatment	Treatment Discontinuation
Diarrhea/Colitis	2-3	Toxicity resolves to Grade 0-1	Toxicity does not resolve within 12 weeks of last dose or inability to reduce corticosteroid to 10 mg or less of prednisone or equivalent per day within 12 weeks
	4	Permanently discontinue	Permanently discontinue
AST, ALT, or Increased	2	Toxicity resolves to Grade 0-1	Toxicity does not resolve within 12 weeks of last dose
Bilirubin	3-4	Permanently discontinue (see exception below) ^a	Permanently discontinue
Type 1 diabetes mellitus (if new onset) or Hyperglycemia	T1DM or 3-4	Hold pembrolizumab for new onset Type 1 diabetes mellitus or Grade 3-4 hyperglycemia associated with evidence of beta cell failure	Resume pembrolizumab when patients are clinically and metabolically stable
Hypophysitis	2-4	Toxicity resolves to Grade 0-1. Therapy with pembrolizumab can be continued while endocrine replacement therapy is instituted	Toxicity does not resolve within 12 weeks of last dose or inability to reduce corticosteroid to 10 mg or less of prednisone or equivalent per day within 12 weeks
Hyperthyroidis m	3	Toxicity resolves to Grade 0-1	Toxicity does not resolve within 12 weeks of last dose or inability to reduce corticosteroid to 10 mg or less of prednisone or equivalent per day within 12 weeks
	4	Permanently discontinue	Permanently discontinue
Hypothyroidis m		Therapy with pembrolizumab can be continued while thyroid replacement therapy is instituted	Therapy with pembrolizumab can be continued while thyroid replacement therapy is instituted
Infusion	2 ^b	Toxicity resolves to Grade 0-1	Permanently discontinue if toxicity develops despite adequate premedication
Reaction	3-4	Permanently discontinue	Permanently discontinue
Pneumonitis	2	Toxicity resolves to Grade 0-1	Toxicity does not resolve within 12 weeks of last dose or inability to reduce corticosteroid to 10 mg or less of prednisone or equivalent per day within 12 weeks
	3-4	Permanently discontinue	Permanently discontinue
Renal Failure or Nephritis	2	Toxicity resolves to Grade 0-1	Toxicity does not resolve within 12 weeks of last dose or inability to reduce corticosteroid to 10 mg or less of prednisone or equivalent per day within 12 weeks
	3-4	Permanently discontinue	Permanently discontinue
All Other Drug- Related Toxicity ^c	3 or Severe	Toxicity resolves to Grade 0-1	Toxicity does not resolve within 12 weeks of last dose or inability to reduce corticosteroid to 10 mg or less of prednisone or equivalent per day within 12 weeks
Tomony	4	Permanently discontinue	Permanently discontinue

Note: Permanently discontinue for any severe or Grade 3 drug-related AE that recurs or any life-threatening event.

Dosing interruptions are permitted in the case of medical / surgical events or logistical reasons not related to study therapy (e.g., elective surgery, unrelated medical events, patient vacation, and/or holidays). Subjects should be placed back on study therapy within 3 weeks of the scheduled interruption, unless otherwise discussed with the Sponsor. The reason for interruption should be documented in the patient's study record.

^a For patients with liver metastasis who begin treatment with Grade 2 AST or ALT, if AST or ALT increases by greater than or equal to 50% relative to baseline and lasts for at least 1 week then patients should be discontinued.

b If symptoms resolve within one hour of stopping drug infusion, the infusion may be restarted at 50% of the original infusion rate (e.g., from 100 mL/hr to 50 mL/hr). Otherwise dosing will be held until symptoms resolve and the subject should be pre-medicated for the next scheduled dose; Refer to— Infusion Treatment Guidelines for further management details.

^c Patients with intolerable or persistent Grade 2 drug-related AE may hold study medication at physician discretion. Permanently discontinue study drug for persistent Grade 2 adverse reactions for which treatment with study drug has been held, that do not recover to Grade 0-1 within 12 weeks of the last dose.

4.3.2 Timing of Dose Administration

Trial treatment should be administered on Day 1 of each cycle after all procedures/assessments have been completed as detailed on the Trial Flow Chart (Section 5.0). Trial treatment may be administered up to 3 days before or after the scheduled Day 1 of each cycle due to administrative reasons.

All trial treatments will be administered on an outpatient basis.

Pembrolizumab 200 mg will be administered as a 30 minute IV infusion every 3 weeks. Sites should make every effort to target infusion timing to be as close to 30 minutes as possible. However, given the variability of infusion pumps from site to site, a window of -5 minutes and +10 minutes is permitted (i.e., infusion time is 30 minutes: -5 min/+10 min).

The Pharmacy Manual contains specific instructions for the preparation of the pembrolizumab infusion fluid and administration of infusion solution.

4.3.3 Trial Blinding/Masking

This is an open-label trial; therefore, the Sponsor, investigator and subject will know the treatment administered.

4.4 Registration or Treatment Allocation

Assignment of the treatment/allocation number will be directed by the Lead Study Coordinator at Johns Hopkins. All enrolled subjects will be allocated to receive pembrolizumab 200mg Q3W as monotherapy in an unblinded fashion.

4.5 Stratification

No stratification based on age, sex or other characteristics will be used in this trial.

4.6 Concomitant Medications/Vaccinations (allowed & prohibited)

Medications or vaccinations specifically prohibited in the exclusion criteria are not allowed during the ongoing trial. If there is a clinical indication for one of these or other medications or vaccinations specifically prohibited during the trial, discontinuation from trial therapy or vaccination may be required. The investigator should discuss any questions regarding this with the Merck Clinical team. The final decision on any supportive therapy or vaccination rests with the investigator and/or the subject's primary physician.

4.6.1 Acceptable Concomitant Medications

All treatments that the investigator considers necessary for a subject's welfare may be administered at the discretion of the investigator in keeping with the community standards of medical care. All concomitant medication will be recorded on the case report form (CRF) including all prescription, over-the-counter (OTC), herbal supplements, and IV medications

and fluids. If changes occur during the trial period, documentation of drug dosage, frequency, route, and date may also be included on the CRF.

Palliative and supportive care is permitted during the course of this trial for underlying medical conditions and the management of symptoms. Major surgery for tumor control or symptom management is not permitted during the study or within 3 weeks of study commencement, as outlined in section 4.2.7. Palliative radiotherapy is permitted if considered medically necessary by the treating physician as long as the lesion is not the patient's sole measurable lesion on brain or spine MRI or a defined target lesion in the body by RECIST 1.1, as detailed in section 4.2.6. Trial therapy should be held during the course of palliative radiation, and should be resumed no early than the next schedules dose of trial therapy. The specifics of the radiation treatment given, including location, will be recorded. Additionally, patients who receive radiation therapy will be analyzed separately to assess the potential impact of radiation therapy on clinical outcomes.

All concomitant medications received within 28 days before the first dose of trial treatment and 30 days after the last dose of trial treatment should be recorded. Concomitant medications administered after 30 days after the last dose of trial treatment should be recorded for SAEs and ECIs as defined in Section 6.2.

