4.1.5.1 Efficacy Endpoints

4.1.5.1.1 Primary Endpoint:

The primary efficacy endpoint is to evaluate CNS response with pembrolizumab in patients with LMD from solid tumors. CNS response will be defined either as radiologic response, cytologic response, or clinical response, whichever is easier to assess. Radiologic response will be defined as a reduction in size of a measurable lesion on a contrast-enhanced MRI scan of the brain. Cytologic response will be defined as a negative CSF cytology result in 2 consecutive samples, in patients who have initial positive cytology prior to treatment, or a clinical response, defined as an improvement in objective neurologic signs or symptoms attributable to LMD (Table 8). Response assessment is detailed in section 6.1.2.7.

4.1.5.1.2 Secondary Endpoints:

- **1. CNS Progression-free Survival:** A secondary endpoint of this study is to evaluate CNS-PFS, which will be defined as the time from study enrollment until CNS progression (radiologic, cytologic or clinical), or death, whichever occurs first. CNS progression will be classified as radiologic (determined by contrast-enhanced MRI scan), cytologic (determined by pathologic assessment of CSF cytology including cell count, differential, glucose) or clinical progression (defined as new objective neurologic signs or symptoms, attributable to LMD), as detailed in section 6.1.2.7.
- 2. **Overall Survival:** A secondary endpoint of this study is to evaluate OS, which will be defined as the time from study enrollment until death from any cause. Deaths from progressive disease will be stratified as related to CNS progression, related to systemic progression, or both.

8A

3. **Safety:** Safety will be evaluated according to the National Cancer Institute Common Terminology Criteria for Adverse Events (NCI CTCAE) version 4.0^{27} safety will be determined by the number of treatment-related toxicities of > grade 3 severity by CTCAE Version 4.0.

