7. STATISTICAL ANALYSIS PLAN

7.1. Statistical Analysis Plan Summary

Key elements of the statistical plan are summarized in Table 12 below. A comprehensive plan is detailed in section 7.2

Table 12: Statistical Overview

Study Design Overview	Open-label, single arm phase II study of pembrolizumab in patients with advanced solid tumors with leptomeningeal carcinomatosis (LMD)
Treatment Assignment	pembrolizumab 200mg Q3W
Analysis Population	Eligible patients who receive at least one dose of pembrolizumab
Primary Endpoint	CNS response at 12 weeks based on either radiologic, cytologic or clinical evidence
Statistical Methods for Key Efficacy Analyses	The proportion of CNS response and associated 95% exact confidence interval will be provided
Statistical Methods for	Descriptive analysis based on Clopper-Pearson's exact binomial confidence interval method.
Key Safety Analyses	
Multiplicity	N.A.
Sample Size and Power	No formal statistical inference will be provided. The proposed sample size will provide appropriate estimation precision for the primary efficacy endpoint.

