7.2.5. Secondary Efficacy Endpoints

1. CNS Progression-Free Survival (PFS)

PFS is defined as the time from first day of study treatment until date of progression. Progression will be stratified into CNS progression (radiologic or cytology or clinical). CNS radiologic progression will be assessed by MRI criteria, CNS cytologic progression will be determined pathologically, and neurologic progression will be determined as per section 6.1.2.7 and Table 8 respectively. PFS will be calculated using the Kaplan-Meier method.

2. Overall Survival

Overall survival will be defined as the date of study entry until date of death from any cause. Cause of death will be recorded.

3. Safety

The primary safety objective of this trial is to characterize the safety and tolerability of pembrolizumab in subjects with LMD. The primary safety analysis will be based on subjects who experienced toxicities as defined by CTCAE, Version 4.0 criteria (Appendix 2). The attribution to drug, time-of-onset, duration of the event, its resolution, and any concomitant

medications administered will be recorded. AEs will be analyzed including but not limited to all AEs, SAEs, fatal AEs, and laboratory changes. Furthermore, specific immune-related adverse events (irAEs) will be collected and designated as immune-related events of clinical interest (ECIs) as described in Section 6.2.3.2

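### The separate analysis of irradiated patients in 4.6.1 groups them by a post-baseline event, so it cannot show what radiation does to OS or CNS-PFS (minor)

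*Combined protocol and SAP*

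**What the plan says.** Section 4.6.1 governs treatment during the study. It states that "Palliative radiotherapy is permitted if considered medically necessary by the treating physician", with limits on which lesions may be treated, and that "Trial therapy should be held during the course of palliative radiation" and resumed afterwards. It then adds that "patients who receive radiation therapy will be analyzed separately to assess the potential impact of radiation therapy on clinical outcomes". It does not say which outcomes, which comparison, or which period of radiation counts.

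The plan's time-to-event outcomes all start before on-study radiation:

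- OS in 4.1.5.1.2: "which will be defined as the time from study enrollment until death from any cause". In 7.2.5: "Overall survival will be defined as the date of study entry until date of death from any cause".
- CNS-PFS in 4.1.5.1.2: "the time from study enrollment until CNS progression (radiologic, cytologic or clinical), or death, whichever occurs first". In 7.2.5: "PFS is defined as the time from first day of study treatment until date of progression".

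Section 7.2.1 plans Kaplan-Meier curves for both. Section 7 does not mention the radiation analysis, and gives no landmark or time-dependent classification. Table 12 defines the analysis population as "Eligible patients who receive at least one dose of pembrolizumab" and says that no formal inference will be made.

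**The concern.** Membership of the irradiated group is settled by something that happens after the clock starts. A patient must be alive to be irradiated, so the time from entry to radiation is survival that this group cannot fail to have. Patients who die before they could be irradiated count as non-irradiated. CNS-PFS is conditioned in a similar way, because 4.9 makes CNS progression a reason for discontinuation from the trial. With an expected median survival of 3-6 months (4.1.4.5), a wait of some weeks is a large part of follow-up.

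A second selection acts at the same time. Radiation is given when the treating physician judges it necessary, so irradiated patients may be sicker. That pushes their survival down. An analysis described as assessing radiation's impact would mix both biases with any real effect, and a reader could take the curves as evidence about radiation, or about pembrolizumab without it.

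**Working it through.** The plan gives no figure for the radiation analysis. Its sample size does reproduce: 16 / (1 - 0.10) = 17.8, rounded up to 18 (7.2.1).

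**1. Survivor effect alone, one case by hand.** From the plan: median OS 3-6 months; 4.5 is used here. Assumed, since the plan gives no radiation rate: exponential survival, exponential time to radiation with median 4 months, radiation only in the first 3 months, timing unrelated to prognosis, no effect of radiation.

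- Death rate d = ln 2 / 4.5 = 0.1540 per month. Radiation rate r = ln 2 / 4 = 0.1733. Sum s = 0.3273.
- Share irradiated = (r/s)(1 - exp(-3s)) = 0.5294 × 0.6254 = 0.331.
- Mean wait to radiation among the irradiated = 1/s - 3·exp(-3s)/(1 - exp(-3s)) = 3.055 - 1.797 = 1.258 months.
- Mean OS, irradiated = 1.258 + 1/d = 1.258 + 6.492 = 7.750 months.
- Mean OS, never irradiated = (6.492 - 0.331 × 7.750) / 0.669 = 5.87 months.
- Apparent death-rate ratio = 5.87 / 7.75 = 0.76, although the true ratio is 1. Simulation with follow-up cut at 24 months gives 0.75, with median OS 5.8 v 3.7 months.

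**2. Same case, patients counted as non-irradiated until radiation starts.** Per patient enrolled:

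- Irradiated: 0.331 deaths over 0.331 × 6.492 = 2.150 person-months, a rate of 0.154.
- Non-irradiated: 0.669 deaths over 0.669 × 5.87 + 0.331 × 1.258 = 4.34 person-months, a rate of 0.154.
- Ratio 1.00. The survivor effect is gone.

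**3. Range under the same model (simulation, 24-month cut).**

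| Median OS (months) | Ever/never ratio, median time to radiation 2, 4, 8 months | Time-dependent ratio |
|---|---|---|
| 3 | 0.60, 0.69, 0.73 | 1.00 |
| 4.5 | 0.67, 0.75, 0.79 | 1.00 |
| 6 | 0.72, 0.79, 0.82 | 1.00 |

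A different timing model (25% of patients are candidates, radiation uniform over 3 or 6 months, given only if alive) gives 0.59-0.82.

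**4. Adding radiation for symptoms.** Still with no radiation effect:

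- Milder selection: half the patients are sicker, with a death hazard 1.5-3 times higher, and are irradiated at three times the rate. Ever/never ratio 0.82-0.85; time-dependent ratio 1.12-1.20.
- Stronger selection: hazard 2-4 times higher, candidates 37.5% v 12.5% or 45% v 5%, radiation uniform over 1.5 or 3 months, overall median OS 3-6 months. Ever/never ratio 0.85-1.87; time-dependent ratio 1.19-2.12.

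The ever/never ratio can therefore fall on either side of 1. Time-dependent classification removes the survivor effect but leaves the indication effect, which then makes radiation look harmful.

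**5. What 16-18 patients can show.** In simulated 18-patient trials under the model of step 3 (median time to radiation 4 or 8 months), radiation looked better in 59-77% of trials, against about 50% without bias. Under the uniform model about 2-3 of 16 patients are irradiated. At a week-6 landmark only about 0.7-1.6 irradiated patients per 16 would remain, too few for a landmark comparison.

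All of these figures are for OS. No CNS-PFS figure was computed.

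**The case against.** The sentence in 4.6.1 says only clinical outcomes. It names no endpoint, contrast or test, and a descriptive listing of irradiated patients would satisfy it. Table 12 disclaims formal inference. With so few patients, noise exceeds the bias: in 16-patient trials the 5-95% range of the naive ratio is about 0.30-2.6. Section 4.6.1 also refers back to 4.2.6, which covers radiation before study therapy, where there is no survivor conditioning.

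Much of this stands and sets the severity. It does not remove the point. OS and CNS-PFS are the plan's only time-to-event efficacy outcomes, the sentence sits among the on-study rules, and its stated purpose is to assess an effect.

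Two stronger readings are tempting and are not supported:

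- *The response rate is inflated.* If irradiated non-responders left the denominator, 3/16 = 18.8% would become 3/14 = 21.4% or 3/12 = 25.0%. But 4.6.1 does not say that anyone is removed, Table 12 and 7.2.1 keep every eligible dosed patient, and the arithmetic assumes that every removed patient failed.
- *The split will show a false benefit of radiation and depress the survival read as pembrolizumab alone.* This follows only if radiation is unrelated to prognosis. Under selection for symptoms the sign can reverse. Nor do all early deaths fall in the non-irradiated group: with radiation uniform over 3 months, about 11-12% of deaths before month 3 are in the irradiated group.

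**Conclusion.** The point holds as a minor one. For on-study radiation, an ever/never split from enrollment or first dose contains guaranteed survival time. Taken alone, that produces a null death-rate ratio of about 0.6-0.8 at the plan's 3-6 month median survival. The size rests on assumed radiation shares and timing, because the plan gives none; the existence of the bias does not. Selection of symptomatic patients works in the opposite direction by an unknown amount, so the net direction cannot be stated and the split cannot show radiation's impact. The primary response estimate and the overall OS and CNS-PFS curves do not depend on this sentence, and no claim about an inflated response rate is made.

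**What to change.** Amend 4.6.1 and add matching text to 7.2.5:

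- All eligible dosed patients stay in the primary response, CNS-PFS and OS analyses whatever radiation they receive, consistent with Table 12.
- Radiation before first dose is a baseline subgroup. State the period that counts as on-study radiation for the analysis; 4.6.2 lists no prohibited therapies in post-treatment follow-up, so an ever-irradiated group could otherwise include later radiation.
- On-study radiation is described in a patient-level listing: site, start date and outcome.
- If any association with OS or CNS-PFS is shown, patients count as non-irradiated until the radiation start date. A fixed landmark is not advised, given the numbers in step 5 of the working.
- Drop the wording about impact, and state that confounding by indication remains and the result is descriptive.

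The cost is protocol and SAP wording and a little more analysis work. Section 4.6.1 already requires the radiation details to be recorded; the start date must be among them. No extra patients or visits are needed. The downside is that the result stays purely descriptive.
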